Conjunctival hyperemia is a common adverse reaction of PGAs, mainly due to vasodilation in sclera and conjunctiva. [37] Several studies place the occurrence of conjunctival hyperemia between 27% and 49%. [32, 38, 39]

Other reactions commonly attributed to PGAs are the growth and darkening of the eyelashes and the darkening of the iris. [40, 41, 42]

There have been some reports of cases of potential risk of cystoid macular edema in pseudophakic patients using PGAs. [43, 44] Nevertheless, this relationship has not been confirmed with appropriate scientific literature. [37]

Cases of anterior uveitis related to the use of travoprost have been reported, which remit when the travoprost is discontinued and with the administration of topical steroids. [45]

5.2.4 Risk benefit evaluation.

5.2.4.1 Known potential risks.

The frame of reference of travoprost places it as a safe molecule, with a known safety and tolerability profile. PRO-179 shares the same active principle, in the same concentration as Travatan®. The main adverse effects, such as conjunctival hyperemia and alterations in eyelashes and eyelids are reversible. The effects on changes in iris coloring appear in the first 6 to 8 months of treatment.

Pre-clinical studies of PRO-179 compared to Travatan® have been conducted, where a safety and toxicity profile has been demonstrated, as well as similar bioavailability in a model of albino rabbits New Zealand. [46, 47]

5.2.4.2 Known potential benefits.

The effectiveness of travoprost has been previously documented in the literature. Generic drugs help reduce the costs of treatments by generating direct competition with the innovator.

The present study does not represent a direct benefit for patients; nevertheless, neither a potential risk in the medium or long term; due to the antecedents that place travoprost as safe. In the same way, the procedures proposed to be carried out during the study do not represent an additional risk to the subject.

5.3 Statement of the problem.

Chronic diseases, such as glaucoma, pose a significant economic burden to the patient and society. Due to this the health authorities support the development of generic medicines, once the patent of the innovator has expired. The above would mean obtaining the drugs at a lower cost.

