The return will be made by the research center when the sponsor indicates it. Prior to the return, the research center must make a count of the assigned medication and the remaining medication, with the aim of creating an inventory which serves for the final filling of the medication return form.

6.4 Delay variables.

6.4.1 Security variables.

6.4.1.1 Primary outcome variables.

- Incidence of adverse events.

6.4.1.2 Variables of primary outcome of tolerability.

- ICO score.

6.4.1.3 Secondary outcome variables.

- Changes in visual ability.
- Changes in corneal and conjunctival staining with lysine green.
- Changes in corneal and conjunctival staining with fluorescein.
- Changes conjunctival hyperemia.
- Incidence of chemosis.
- Incidence of alterations in the results of laboratory tests.
- Incidence of alterations in the FC.
- Incidence of alterations in the RF.
- Incidence of alterations in the TAS.

6.4.2 Exploratory variables.

- Changes in IOP.

6.4.3 Methods and scales to be used for the measurement of the variables.

Variable	Kind	Unit (Symbol)	Method of measurement	Normal value	Evaluation time	Statistical test
Primary						
Adverse events	Discreet Categorical rating	Number of cases (n) Present/absent	Count Observation	0 Absent	VB, V1, VF y LLS	Mann-Whitney U χ^2 o Fisher's exact
ICO score	Discreet	Points	Questionnaire	NA	VB, VF	Mann-Whitney U
Secondary						
Visual ability	Discreet	Fraction	Snellen Primer	1	VB, V1 y VF	Mann-Whitney U
Corneal and conjunctival staining with fluorescein	Ordinal	Degrees	Direct observation with slit lamp and cobalt blue filter, Oxford scale graduation	0	VB, V1 y VF	χ^2 or Fisher's exact

Variable	Kind	Unit (Symbol)	Method of measurement	Normal value	Evaluation time	Statistical test
Corneal and conjunctival staining with lysamine green	Ordinal	degrees	Direct observation with slit lamp, Oxford scale graduation	0	VB, V1 y VF	χ^2 or Fisher's exact
Conjunctival hyperemia	Ordinal	Normal / Very Light / Mild / Moderate / Severe	Direct observation. Classification of Efron.	Normal	VB, V1 y VF	χ^2 or Fisher's exact
Chemosis	Categorical rating	Present / absent		Absent	VB, V1 y VF	χ^2 or Fisher's exact
FC	Discreet	eats per minute (l / m)	Auscultation with stethoscope	60 to 100	VB, V1 y VF	Mann-Whitney U
FR	Discreet	Breaths per minute (r / m)	Auscultation with stethoscope	12 to 24	VB, V1 y VF	Mann-Whitney U
TAS	Discreet	Millimeters of mercury (mmHg)	Measurement with sphygmomanometer	90-120/ 60-80	VB, V1 y VF	Mann-Whitney U

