- Adverse events: see 6.4.3.5 Presence of adverse events.
- Review of laboratory tests: see Baseline visit.

6.5.1.6 Early termination visit.

If the research subject's participation ends earlier than scheduled, due to an adverse event or any other situation, an unscheduled visit will be made, which will serve as the final visit. In case the subject refuses to attend, the last visit made will be taken as final. Subsequently, the security call will be made in the normal time established.

6.5.2 Diagram of the study.

[figure not shown]
[figure not shown]

Figure 3. Horizontal diagram of the study.

* Baseline measurements can be taken from those made during the screening visit. It is the investigator's prerogative to perform them again at the baseline visit.

Figure 4. Vertical diagram of the study.

6.6 Sample size.

A total size of 24 subjects is estimated, divided into 2 intervention groups (12 subjects per group). A 45-day enrollment time is expected for the total sample.

6.6.1 Calculation of the sample size.

Although there are no references on the calculation of sample size in phase I studies, the incidence of ocular adverse events was considered, basing the calculation on the presence of conjunctival hyperemia.

Based on the following work hypothesis:

$$H_0 = p_A - p_B \leq \delta$$

$$H_1 = p_A - p_B > \delta$$

The formula for proportions was used (Chow et al., 2008) [62]:

$$n_B = \left(\frac{p_A(1-p_A)}{k} + p_B(1-p_B) \right) \left(\frac{z_{1-\alpha} + z_{1-\beta}}{p_A - p_B - \delta} \right)^2$$

The study by Mishra et al, whose objective was to compare the efficacy and safety of latanoprost, bimatoprost, travoprost and timolol in the reduction of intraocular pressure (IOP) and the incidence of adverse events in patients with primary angle glaucoma, was used as a reference open (GPA). [63] This was a prospective, unicentric study in 140 patients with recent diagnosis of POAG who were assigned to some intervention (n = 35 per arm / both eyes). Follow-up at 2, 6 and 12 weeks. The main safety variable was the presence of adverse events (AD). OAEs were observed in 41.9% (13/31) of patients treated with travoprost with an incidence of conjunctival hyperemia of 12.9%. The EA reported were: conjunctival hyperemia, dry eye, discomfort and keratitis.

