- Intra-group analysis: will be determined by the Wilcoxon rank test, for quantitative variables [65]
- Inter-group analysis: will be determined by the Mann-Whitney U test Kruskal-Wallis. This non-parametric test will be used to test whether a group of data comes from the same

population. Intuitively, it is identical to the ANOVA with the data replaced by categories using the student's t statistic.

The level of difference to consider significance will be an alpha of 0.05 or less.

The result of nominal and ordinal qualitative variables will be presented in frequencies, proportions and percentages, see table 3 (section 6.4.3).

The statistical analysis to identify significant differences of the qualitative variables will be done creating 2x2 contingency tables and it will be done in the following way:

- Intra-group difference: McNemar test [66]. Which is applied to 2×2 contingency tables with a dichotomous trait, with pairs of matched subjects, to determine if the marginal frequencies of row and column are equal (marginal homogeneity).
- Inter-group difference: Pearson's χ^2 test (or Fisher's exact).

The level of difference to consider significance will be an alpha of 0.05 or less.

For the reporting of adverse events all eyes of those participants who were randomly assigned to an intervention group after the baseline visit will be considered. The results will be expressed in number of cases (eyes).

The final report of the results will be shown in tables or graphs, as appropriate.

It will be considered that the investigational drug is safe and tolerable when there are no clinical and statistical differences in all the variables of primary outcome, with respect to its comparators.

Those subjects who comply with an adherence greater than 60% will be included in the statistical analysis to meet the objective of the study, taken from the subject's diary. It was considered that from the minimum dose necessary to obtain a pharmacological effect (hypotensive / 1 application per day) and the presence of adverse events (exposure) is sufficient to meet the overall design objective, according to the pharmacological characteristics of the IP.

8.3.2 Additional analyzes.

No additional analyzes are contemplated to those previously described. Nevertheless, these may be performed if during the conduction of the study it is required to analyze specific safety aspects of any intervention, maintaining the blinding until the end of the study.

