Circle your answer for each question.

Example: The last week, how often your eyes were red?

Never	0	1	2	3	4	5	Always
							6

There are no correct or incorrect answers. Do not take too much time in each question.

1 The last week, how often your eyes felt dry?

Never	0	1	2	3	4	5	Always
							6

When your eyes felt dry, usually, how intense was the sensation?

I have not	Never	Always					
felt it	0	1	2	3	4	5	6

2 The last week, how often your eyes felt sandy?

Never	0	1	2	3	4	5	Always
							6

When your eyes felt sandy, usually, how intense was the sensation?

I have not	Never	Always					
felt it	0	1	2	3	4	5	6

3 The last week, how often your eyes felt throbbing?

Never	0	1	2	3	4	5	Always
							6

When your eyes felt throbbing, usually, how intense was the sensation?

I have not	Never	Always					
felt it	0	1	2	3	4	5	6

4 The last week, how often your eyes felt tired?

Never	0	1	2	3	4	5	Always
							6

When your eyes felt tired, usually, how intense was the sensation?

I have not	Never	Always					
felt it	0	1	2	3	4	5	6

5 The last week, how often your eyes felt sore?

Never	0	1	2	3	4	5	Always
							6

When your eyes felt sore, usually, how intense was the sensation?

I have not felt it	0	1	2	3	4	5	Severe
							6

6 The last week, how often your eyes felt itchy?

Never	0	1	2	3	4	5	Always
							6

When your eyes felt itchy, usually, how intense was the sensation?

I have not felt it	0	1	2	3	4	5	Severe
							6

13.2 Efron scale for conjunctival hyperemia.

13.3 Oxford Scale.

PANEL	Grade	Criteria
A	0	Equal to or less than panel A
B	I	Equal to or less than panel B, greater than A
C	II	Equal to or less than panel C, greater than B
D	III	Equal to or less than panel D, greater than C
E	IV	Equal to or less than panel E, greater than D
>E	V	Greater than panel E

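### Ordered hyperemia and staining grades are tested in 2x2 tables with no stated split, and the between-arm test of the primary comfort score leaves out its collected baseline

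*Combined protocol and SAP*

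**What the plan says.** Section 8.3.1 puts ordinal variables under the qualitative heading: "The result of nominal and ordinal qualitative variables will be presented in frequencies, proportions and percentages". It then prescribes one method for qualitative variables: "The statistical analysis to identify significant differences of the qualitative variables will be done creating 2x2 contingency tables", with McNemar within arm and Pearson chi-square or Fisher between arms.

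Table 3 (section 6.4.3) types conjunctival hyperemia and both stainings as ordinal and assigns them chi-square or Fisher. Hyperemia has five levels, "Normal / Very Light / Mild / Moderate / Severe". Staining uses the Oxford scale of annex 13.3, six ordered grades defined by reference panels (grade I, for example, is "Equal to or less than panel B, greater than A").

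Section 6.4.1.3 names the outcome as "Changes conjunctival hyperemia". The plan does not say whether the between-arm table compares change or the grade at the visit.

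Section 6.6.1 sizes the trial on this sign, "basing the calculation on the presence of conjunctival hyperemia", and cites a glaucoma study "with an incidence of conjunctival hyperemia of 12.9" per cent. Section 5.2.3 gives a higher range: "Several studies place the occurrence of conjunctival hyperemia between 27% and 49" per cent.

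The Ocular Comfort Index (ICO) is a primary outcome, timed at day 11 in the synopsis. Table 3 collects it at the baseline and final visits. Its between-arm test is an unadjusted Mann-Whitney; the baseline enters only the within-arm Wilcoxon test of section 8.3.1.

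**The concern.** A five- or six-level scale cannot enter a 2x2 table, or McNemar's test, until someone decides where to cut it. Table 3's normal values (Normal; 0) suggest normal v abnormal, but nothing calls them a cut-point. The analysis therefore cannot be run as written without a later choice, and that choice can change the result. Hyperemia is a common reaction to this drug class and the sign behind the sample size, so its analysis should not be left open. Collapsing also treats a move from normal to severe like a move from normal to very light.

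For the ICO the issue is unused information. It is inside the decision rule of section 8.3.1, under which the product is accepted when no primary outcome differs. Low sensitivity there works in favour of acceptance.

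**Working it through.** The plan gives no power figure for the graded signs or the ICO, so there is none to reproduce. The documents give no grade distribution, shift, correlation or floor; all of these are assumptions below.

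**Inputs.** 12 subjects per arm (6.6.1); two-sided 0.05 (8.3.1 gives alpha 0.05); one value per subject, since the plan states no unit for graded signs. Control-arm rates of grade 1 or above: 12.9% (6.6.1), 27% and 49% (5.2.3). Using these rates for healthy subjects over 10 days is an assumption; the 12.9% comes from glaucoma patients followed for 12 weeks.

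**Model for grades.** Latent normal score with SD 1, five grades, cuts 0.8 SD apart, all baselines at grade 0. First cut c1 = Φ⁻¹(1 − control rate). In the arm shifted by 1 SD, P(grade ≥ k) = 1 − Φ(ck − 1).

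| Control rate | c1 | Grade ≥1, control v shifted | Grade ≥2, control v shifted |
|---|---|---|---|
| 12.9% | 1.131 | 0.129 v 0.448 | 0.027 v 0.176 |
| 27% | 0.613 | 0.270 v 0.651 | 0.079 v 0.340 |
| 49% | 0.025 | 0.490 v 0.835 | 0.205 v 0.569 |

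**Power.** For a 2x2 table, power is the sum of Bin(a; 12, p1) × Bin(b; 12, p0) over all pairs (a, b) whose p-value is at most 0.05. Mann-Whitney (tie- and continuity-corrected) was simulated with 50,000 trials per setting.

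| Control rate | Mann-Whitney on grades | Fisher, ≥1 | Uncorrected Pearson, ≥1 | Fisher, ≥2 |
|---|---|---|---|---|
| 12.9% | 39% | 25% | 41% | 3% |
| 27% | 51% | 35% | 52% | 18% |
| 49% | 57% | 29% | 45% | 32% |

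With no true difference, Mann-Whitney rejects in 2 to 4% of trials. Pearson at grade ≥1 rejects in 2.4, 4.6 and 6.4% at the three rates, so it is slightly liberal at 49%.

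With a 0.7-SD shift, Mann-Whitney / Fisher / Pearson at grade ≥1 give about 20/10/20%, 26/16/29% and 32/16/28%.

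**Choice between Pearson and Fisher.** The plan states no rule. Under the common one (Pearson when all expected counts reach 5, otherwise Fisher; an assumption), the planned test has about 26, 45 and 32% power at the 1-SD shift. The rank test's lead is then 39 − 26 = 13, 51 − 45 = 6 and 57 − 32 = 25 points.

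**When the effect is not a common shift.** Suppose one arm has grades in proportions 60/20/12/6/2% and the other 15/65/12/6/2%, so that only the move from normal to the first grade differs. Exact Mann-Whitney then has 39% power, against 52% for Fisher and 70% for Pearson at grade ≥1.

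**Grade at visit or change.** With 10 to 25% abnormal at baseline and a 1-SD shift, Mann-Whitney on change v on visit grade gives 44% v 51% (control rate 27%, 25% abnormal, correlation 0.3) and 66% v 57% (49%, 25%, correlation 0.6). Change loses at low correlation and gains at high.

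**ICO.** Bivariate normal baseline and day 11, 1-SD effect, 12 per arm:

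| Baselines at zero | Mann-Whitney, day 11 | Rank ANCOVA at correlation 0.3 / 0.5 / 0.7 |
|---|---|---|
| none | about 60% | 64 / 71 / 84% |
| 50% | 58% | 61 / 67 / 78% |
| 72% | 52–53% | 55 / 58 / 66% |
| 85% | 43–44% | 44 / 46 / 51% |

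With no true effect, rank ANCOVA rejects in 2.7 to 5.3% of trials. With no floor, Mann-Whitney on the change score has 46% power at correlation 0.3, below the unadjusted test.

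**The case against.** The strongest reply is that the plan allows Pearson as well as Fisher, and that normal v abnormal is the obvious split. At that split uncorrected Pearson equals or slightly beats the rank test at control rates of 12.9 and 27%. This stands. A reader might infer that a rank test is always more sensitive than the planned table; the documents give no grade distribution that would support this, and the normal-to-first-grade example reverses it. What remains is the loss against Fisher, which small expected counts will often call for at 12 per arm, and the loss at a poor split.

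A second reply is that the analysts are blinded to arm (8.3.1). That limits a choice of split by product. It does not close the gap: groups are coded by number, so a difference between codes is visible under any split, and the hoped-for result is no difference in either direction. Nothing in the documents suggests that a split would be chosen this way.

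Third, the consequence is limited. Hyperemia and staining grades are secondary, and the decision rule uses primary outcomes only. A reader might infer that the acceptance of PRO-179 turns on the grade analysis; it does not. Hyperemia reported as an adverse event enters the primary incidence through its own Table 3 row.

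Fourth, a reader might infer that the ICO test is wrong. It is valid and matches the named day-11 outcome; the point is only unused sensitivity, and the gain is small if most healthy subjects score zero.

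**Conclusion.** The point holds in a limited form. For hyperemia and staining, the plan discards grade order and leaves the split unstated. At 12 per arm with a common 1-SD shift, the rank test gains 14 (39 − 25), 16 (51 − 35) and 28 (57 − 29) points over Fisher at normal v abnormal, and more over Fisher at grade 2 or above when the control rate is 12.9 or 27%. Against uncorrected Pearson at normal v abnormal there is no gain at those two rates, and about 12 points (57 − 45) at 49%. All of this rests on the assumed latent shift, equal cuts and grade 0 at baseline. The missing split does not rest on any assumption: it follows from the text. The formal conclusion of the trial is unaffected by this part.

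For the ICO, covariate adjustment adds about 4 to 24 points with no floor and about 1 to 7 points with 85% of baselines at zero. It improves a valid test of a primary outcome; it does not correct an error.

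**What to change.** In Table 3 and section 8.3.1:

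- Compare hyperemia and both stainings between arms by tie-corrected Mann-Whitney on one grade per subject (for example the worse eye) at each visit. Give change from baseline as supportive, and use Wilcoxon signed-rank within arm in place of McNemar.
- Keep the frequency tables as description. If a 2x2 test is kept, fix the split in advance as normal v abnormal, say whether it compares visit grade or change, and state when Pearson or Fisher applies.
- Analyse ranked day-11 ICO on arm with ranked baseline ICO as covariate, not as a change score.

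The cost is text edits before unblinding. Mann-Whitney and Wilcoxon are already planned, and the grades and baseline ICO are already collected. There are no added visits, subjects or measurements. The one downside is that rank ANCOVA is a method new to the plan.

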The data will be expressed with measures of central tendency: mean and standard deviation for the quantitative variables. The qualitative variables will be presented in frequencies and percentages. The statistical analysis will be carried out by means of the Mann-Whitney U test for the quantitative variables for the difference between the groups. The difference between the qualitative variables will be analyzed by means of χ^2 (Chi2) or Fisher's exact. An alpha ≤ 0.05 will be considered significant.

1.2 Diagram of the study.

* Baseline measurements can be taken from those made during the screening visit. It is the investigator's prerogative to perform them again at the baseline visit.

1.3 Schedule of the study .

Procedures	Scrutiny D 1 - X ^a	VB D 1	V1 D 5 ± 1	VF D 11 a + 1	LIS D 14 ± 1
CI Signature	X				
Clinic history	X				
Concomitant Medication Evaluation	X	X	X	X	
Urine pregnancy test	X			X	
Vital signs	X	X ¹	X	X	
CV	X	X ¹	X	X	
Integrity of the ocular surface	X	X ¹	X	X	
PIO	X	X ¹	X	X	
Comprehensive ophthalmological evaluation	X	X ^{1,2}	X	X ²	
Eligibility criteria	X	X ^b			
Blood sampling	X			X	
EA evaluation	X	X	X	X	X
Review of laboratory results		X			X
Assignment of Research Product (PI)		X			
Ocular Comfort Index		X		X	
Delivery of the IP and start of intervention		X			
Adherence evaluation			X	X	
Daily delivery of the subject		X	X		
Continuity evaluation of the subject			X		
Return / Evaluation of the subject's Journal			X	X	
Return of IP				X	

- a. The counting visit may be up to 7 days before the baseline, if it exceeds these the subject can not enter.
- b. These criteria will be completed with the results of the laboratory tests and those obtained during the screening visit. 1 They can be taken from the scrutiny visit, it is the prerogative of the PI to measure them again at the baseline visit. 2 Includes subsequent segment valuation.

**Page intentionally left
blank**

2 Content

1.1 SUMMARY	1
1.2 SYNOPSIS	1
1.2 DIAGRAM OF THE STUDY.	4
1.3 SCHEDULE OF THE STUDY .	5
2 CONTENT	7
3 INDEX OF ABBREVIATIONS.	11
4 ADMINISTRATIVE STRUCTURE OF THE STUDY.	13
5 INTRODUCTION	15
5.1 THEORETICAL FRAMEWORK.	15
5.2 BACKGROUND .	15
5.2.1 PHARMACOLOGY OF TRAVOPROST.	15
5.2.1.1 Pharmacokinetics .	16
5.2.1.2 Pharmacodynamics .	16
5.2.2 EFFICIENCY OF TRAVOPROST.	16
5.2.3 SAFETY OF TRAVOPROST.	17
5.2.4 RISK BENEFIT EVALUATION.	17
5.2.4.1 Known potential risks.	17
5.2.4.2 Known potential benefits.	17
5.3 STATEMENT OF THE PROBLEM.	17

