- Compare the safety of PRO-179 with Travatan® by the incidence of chemosis during visits.
- Compare the safety of PRO-179 with Travatan® by means of the incidence of alterations in the results of the laboratory tests on day 11.

- Compare the safety of PRO-179 with Travatan® through the incidence of changes in HR during visits.
- Compare the safety of PRO-179 with Travatan® by means of the incidence of RF alterations during visits.
- Compare the safety of PRO-179 with Travatan® by the incidence of changes in SAD during visits.

5.5.3 Exploratory objectives.

- Compare changes in intraocular pressure during visits.

5.5.4 Hypothesis.

H0 The ophthalmic solution PRO-179 presents a profile of safety and tolerability similar to Travatan® in healthy subjects.

Ha The ophthalmic solution PRO-179 presents a different safety and tolerability profile Travatan® in healthy subjects.

5.6 Design and plan of the study.

Clinical trial, phase I, controlled, of parallel groups, double blind with randomization.

5.6.1 Discussion of the study design.

The design of the study (clinical trial) is considered the highest standard of data quality when looking to explore the effect of an intervention. The phase of pharmacological development (phase I) corresponds to the objective of the study which is to assess safety and tolerability, so that the intervention time is short and the sample size required is less than that of a clinical efficacy trial. The presence of parallel groups allows the comparison between the intervention groups on the outcome variables. Blinding and randomisation allow to reduce biases that are incurred with other designs, eg. selection bias, evaluation bias, among others.

The comparator, Travatan®, has a known safety profile and shares the same active principles in the same concentrations as PRO-179, which is why it was chosen as the best option to compare.

5.6.2 Justification of the posology.

The chosen dosage is one drop every 24 hours at night, this is the indicated and approved dosage for the reference medicine. Clinical studies demonstrate the sufficiency of 1 drop every 24 hours; likewise, they have shown that the administration at night presents less IOP fluctuations during 24 hours, unlike the morning application. [38]

For this phase I study, we do not consider it necessary to expose the research subjects to dosage rates higher than those recommended, since it is not justifiable.

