Calculation: the percentage of AD presented in the group treated with travoprost was considered. Expecting a similar proportion of conjunctival hyperemia due to PGA and healthy subjects. Considering a power of 80%, a significance level of 0.05 (α) and a non-inferiority margin of 5% (δ).

Calculated sample: 20, increasing the calculation by 20% considering possible losses, 25 subjects.

Suggested sample: 12 subjects (24 eyes) per treatment arm.

6.7 Recruitment.

It is essential that, if necessary during the development of this research protocol, the principal investigator requests the approval of the Research Ethics Committee and the Research Committee, as well as the authorization of COFEPRIS, to publish or disseminate in mass media, the invitation to participate in the study to those people who meet the selection criteria.

It is possible to discuss with other health professionals the opportunity for healthy subjects to be evaluated by an ophthalmologist at no cost, as well as cabinet exams that will allow the more accurate determination of their ocular clinical status by participating in a sponsored clinical research protocol by Sophia Laboratories, SA of C.V.

7 Methods. Assignment of the intervention.

7.1 Generation of the allocation sequence.

Two strata corresponding to the intervention groups will be used, which will be balanced for a research center. The allocation will be 1: 1. The generation will be carried out by a third party, authorized by Sophia Laboratories, S.A. of C.V., through its electronic system. The information corresponding to this third party will be found in the file.

7.2 Blinding mechanism.

Blinding will be done by the Department of Clinical Operations of Sophia Laboratories, S.A. of C.V. Which will consist of the elimination of the primary label (commercial) in the case of Travatan® and the placement of a label identical to the other IP. Because the bottle in which Travatan® is packaged differs in color and shape to that used for PRO-179, a masking will be made in the primary packaging which will be identical for the interventions. The subject will have determinedly prohibited to comment with another person that is not the pharmacist aspects related to the primary container (bottle).

7.3 Implementation.

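### The primary adverse-event comparison has no rule for choosing chi-square or Fisher and no named deciding form; per subject at 12 v 12 the two tests split on eight outcomes

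*Combined protocol and SAP*

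**What the plan says.** Three places in the combined protocol and SAP set the test.

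- **Synopsis, statistical methodology.** "The difference between the qualitative variables will be analyzed by means of" chi-square, given as "Chi2) or Fisher's exact".
- **Section 6.4.3, Table 3.** The adverse-event row has two forms, "Number of cases (n) Present/absent". Mann-Whitney U is listed beside the count; chi-square "o Fisher's exact" is listed beside present/absent.
- **Section 8.3.1.** Quantitative variables are compared by Mann-Whitney and qualitative ones by Pearson's "test (or Fisher's exact" in parentheses.

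No expected-count threshold or other selection criterion appears anywhere. On the level, 8.3.1 says: "The level of difference to consider significance will be an alpha of 0.05 or less". Sidedness is not stated for these tests; the alternative hypothesis in 5.5.4 is that PRO-179 "presents a different safety and tolerability profile".

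Section 6.6.1 gives the size: "Suggested sample: 12 subjects (24 eyes) per treatment arm". Section 8.3.1 reports adverse events as numbers of eyes. It judges the product safe and tolerable if no clinical or statistical difference appears on any primary outcome. The sponsor's staff run the analysis, blinded to group.

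**The concern.** Adverse-event incidence is a primary outcome, and failing to find a difference counts towards the safety conclusion. With 12 subjects per arm, chi-square and Fisher are far enough apart for the verdict to depend on which is run, and the plan leaves that open until the data are in hand. Blinding does not remove the problem. A two-sided p-value is the same whichever arm carries which code, so an analyst who cannot identify the arms can still see which test gives the favourable, non-significant answer.

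Fisher, a common default at this size, has its own cost under this decision rule: a test run well below its nominal level misses real differences more often, and here a miss reads as safety.

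**Working it through.** **Inputs.** 12 subjects per arm (6.6.1); level 0.05 (8.3.1); two-sided testing (assumed from 5.5.4); chi-square without continuity correction (assumed). Common event rates for size: 12.9% (hyperemia) and 41.9% (any ocular event) on travoprost in the study cited in 6.6.1, and 27% and 49%, the hyperemia range in 5.2.3.

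The plan gives no error rate for this comparison. Its only calculated figure is the sample size of 20. The formula in 6.6.1 returns it with 12.9% and 41.9% as the two rates: [0.129 × 0.871 + 0.419 × 0.581] × [(1.645 + 0.842)/(0.129 − 0.419 − 0.05)]² = 0.356 × 53.5 = 19.03, rounded up to 20. The plan does not say that this pair was used. It serves below only as an illustration.

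**One split table by hand, 0/12 v 4/12.**
- Pearson: χ² = 24 × (0 × 8 − 12 × 4)² / (12 × 12 × 4 × 20) = 55,296/11,520 = 4.80, p = 0.028.
- Fisher: 2 × C(12,4)/C(24,4) = 2 × 495/10,626, p = 0.093.

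**All splits.** Enumerating all 13 × 13 = 169 tables gives eight pairs (arms interchangeable) on which the verdicts differ. In each, Pearson is significant and Fisher is not.

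| Events per 12 | Pearson p | Fisher p | Smallest expected count |
|---|---|---|---|
| 0 v 4, 8 v 12 | 0.028 | 0.093 | 2.0 |
| 1 v 6, 6 v 11 | 0.025 | 0.069 | 3.5 |
| 2 v 7, 5 v 10 | 0.035 | 0.089 | 4.5 |
| 3 v 8, 4 v 9 | 0.041 | 0.100 | 5.5 |

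**Real size.** For a common rate p, sum Bin(a; 12, p) × Bin(b; 12, p) over the tables with p-value ≤ 0.05.

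| Common rate | Fisher | Pearson |
|---|---|---|
| 12.9% | 0.5% | 2.4% |
| 27% | 1.6% | 4.6% |
| 41.9% | 2.2% | 6.1% |
| 49% | 2.3% | 6.4% |
| Maximum over all rates | 2.3% | 6.4% |

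**Chance of a split.** 1.9% to 4.1% with equal arms at these four rates; 14.4% if the true rates were 12.9% v 41.9%.

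**Alternative test.** Boschloo's test (Fisher's p-value as statistic, maximised over the common rate) has maximum size 4.5% at 12 v 12. Power at the assumed 12.9% v 41.9% is 34.3%, against 20.7% for Fisher and 35.1% for Pearson. Boschloo agrees with Pearson on six of the eight split pairs and differs on 3 v 8 and 4 v 9.

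**Eyes instead of subjects, 24 v 24.** Treated as independent, and truly so, Fisher's size is 2.2% to 2.9% and Pearson's 5.2% to 6.0% at the same four rates. The tests still split; 4 v 11 gives 0.029 v 0.060. With assumed between-eye correlations of 0.5 to 1 but eyes still analysed as independent, Fisher's size becomes 6% to 15% and Pearson's 12% to 22%.

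**The case against.** **The unit is wrong.** The plan reports adverse events in eyes, so a 12 v 12 calculation does not describe it. This stands as a limit on the figures. A reader might infer that Fisher would run at about 2% in the planned analysis; the documents do not support that, because on correlated eyes Fisher can exceed 5%. The missing rule remains at either unit.

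**Mann-Whitney is not a third option on the same data.** This also stands. A reader might see three interchangeable tests, but Table 3 and 8.3.1 tie Mann-Whitney to the count and chi-square or Fisher to present/absent. The gap is narrower: the deciding form is not named.

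**The size claims depend on the rate.** Correct. Pearson exceeds 5% only at middling rates, and Fisher is nearer 0.5% than 2% at 12.9%.

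**The power example is not a planning scenario.** 12.9% and 41.9% are two kinds of event within one travoprost arm, not rates for two products. The 14.4% and the power figures are therefore illustrative only.

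**Convention would settle it.** Using Fisher when an expected count is below 5 would send six of the eight pairs to Fisher and 3 v 8 and 4 v 9 to Pearson, with size 0.5%, 1.8%, 4.1% and 4.9% at the four rates. That would be workable, but the plan does not state it.

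**The choice of test is secondary.** In the illustration Boschloo still misses about two-thirds of real differences, and no test repairs reading non-significance as safety at this sample size. The verdict also rests on clinical differences and on the other primary outcome. All true, and reasons to treat this as an inexpensive correction rather than a fatal flaw.

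**Conclusion.** The point holds in a limited form. The plan fixes neither the test, nor the form, nor clearly the unit that decides the primary adverse-event comparison. For a subject-level comparison at 12 v 12, two-sided 5%, the choice between the two listed tests reverses the verdict on eight outcome pairs. Fisher's real size lies between 0.5% and 2.3% at the rates the protocol cites, which makes the safety conclusion easier to reach; Pearson's lies between 2.4% and 6.4%.

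These results assume two-sided testing, uncorrected chi-square, one outcome per subject and no losses. They do not carry over to eyes, where the error can run the other way. Nothing here shows that a test would in fact be picked for its result. The plan merely does not rule that out. It should be corrected before unblinding, but it does not invalidate the trial.

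**What to change.** In 8.3.1, the synopsis and the adverse-event row of Table 3:

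- State that the deciding comparison is the proportion of subjects, not eyes, with at least one adverse event.
- Replace the open choice for this outcome with one test: two-sided Boschloo's unconditional exact test at 0.05, computed for the numbers of subjects actually analysed.
- Make the Mann-Whitney on event counts and all eye-level counts descriptive.

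A mid-p version of Fisher is an acceptable substitute only if it is defined as subtracting half the probability of all equally probable tables; at 12 v 12 that has Boschloo's rejection region. Subtracting half of the observed table's probability alone gives Fisher's rejection region and gains nothing.

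The cost is a few lines of wording and a short calculation that may have to be done outside SPSS 19, the package named in 8.3.1. No extra subjects or data are needed.
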